22.0 Withdrawal of Subjects*

 \square N/A: This study is not enrolling subjects. This section does not apply.

22.1 Describe **anticipated** circumstances under which subjects may be withdrawn from the research without their consent.

Response:

Subjects may be withdrawn from the study without their consent if the following occur:

- Develop any indication of root resorption
- Develop any periodontal issues during the study
- Develop any health-related issues during the study
- Voluntarily want to leave the study or cease treatment
- Do not come regularly as needed for the study
- Patient becomes pregnant
- 22.2 Describe any procedures for orderly termination.

NOTE: Examples may include return of study drug, exit interview with clinician. Include whether additional follow up is recommended for safety reasons for physical or emotional health.

Response:

The subjects may withdraw their consent and discontinue at any time throughout the study. If a patient decides to withdraw from the study, any collected data of the subject will be destroyed and discarded accordingly.

22.3 Describe procedures that will be followed when subjects withdraw from the research, including retention of already collected data, and partial withdrawal from procedures with continued data collection, as applicable.

Response:

If subjects withdraw from the research, their data will be kept confidential and abide by all privacy regulations. It will not be used in the research study however as the data will not be complete. It will be maintained for approximately 3 years.

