1.0 Study Summary

Study Title	A Comparison of Class II correction using the Carriere Motion Appliance versus an In-Office Sectional Appliance: Treatment Effects and Efficiency
Study Design	Pilot randomized clinical trial
Primary Objective	1. To evaluate total treatment time, in months, from the initial bonding appointment until a Class I molar relationship has been achieved and the appliance has been removed (T1) using either the Carriere Motion Appliance (CMA) or an in-office fabricated sectional appliance
Secondary Objective(s)	To evaluate secondary tooth movements (mm, degrees) and changes in skeletal measurements after Class II molar correction using the either the CMA or an in-office sectional appliance, by comparing lateral cephalometric radiograph measurements and digital study model measurements taken at the Initial Records appointment prior to treatment(T0) and immediately after removal of appliance – when a Class I molar relationship has been achieved (T1)
Research	Class II Correction Appliances: CMA vs. a sectional, in

Page 4 of 49

Intervention(s)/	office fabricated appliance
Investigational	
Agent(s)	
IND/IDE #	N/A
Study Population	12-17Y11M male and female patients
Sample Size	16 per treatment group (N = 32)
Study Duration for	5 months +/- 1 month
individual	
participants	
Study Specific	CMA= Carriere Motion Appliance
Abbreviations/	ss = Stainless-steel
Definitions	Sagittal first approach = correcting the antero-posterior occlusal relationship prior to the leveling and aligning phase of orthodontic treatment Class I molar relationship = The position of the mesiobuccal cusp of the maxillary first permanent molar occludes distally to the buccal groove of the mandibular first molar, and its distal buccal cusp is positioned in the embrasure between the mandibular first and second molars, when in centric occlusion Class II molar relationship = An occlusal relationship where the buccal groove of the mandibular first molar is positioned distal to the mesiobuccal cusp of the maxillary first molar, when in centric occlusion LFH = lower facial height

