12.0 Procedures Involved*

12.1 Provide a description of **all research procedures or activities** being performed and when they are performed once a subject is screened and determined to be eligible. Provide as much detail as possible.

NOTE: This should serve as a blueprint for your study and include enough detail so that another investigator could pick up your protocol and replicate the research. For studies that have multiple or complex visits or procedures, consider the addition of a schedule of events table in in your response.

Response:

Subjects will be recruited patients from the Orthodontics Clinic at the University at Buffalo School of Dental medicine who are undergoing comprehensive orthodontic treatment. Patients a unilateral or bilateral ½ cusp to full-cusp Class II molar relationship with mild-moderate crowding will qualify for participation. At the orthodontic consult appointment, eligible patients will receive information on the study and will be asked to participate. A randomization protocol will be followed in order to assign subjects to 1 of 2 study groups for Class II correction (CMA v. In-office fabricated Class II correction appliance) once the subject and parents have agreed to participate in the study and have filled out consent forms. Initial records will be taken at T0 (intraoral photographs, 3D scan, radiographs) before starting orthodontic treatment.

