28.0 Consent Process

28.1 Indicate whether you will be obtaining consent.

NOTE: This does not refer to consent documentation, but rather whether you will be obtaining permission from subjects to participate in a research study. Consent documentation is addressed in Section 29.0.

\boxtimes	Yes	(If yes, Provide responses to each question in this Section)
	No	(If no, Skip to Section 29.0)

28.2 Describe where the consent process will take place. Include steps to maximize subjects' privacy.

Response:

Consent will take place at the University at Buffalo School of Dental Medicine in the Orthodontic Clinic, in the privacy of a closed-in room outside of the orthodontic clinic. Prospective subjects will be able to voice any questions or concerns with absolute privacy, prior to providing their consent to participate in the study.

28.3 Describe how you will ensure that subjects are provided with a sufficient period of time to consider taking part in the research study.

NOTE: It is always a requirement that a prospective subject is given sufficient time to have their questions answered and consider their participation. See "SOP: Informed Consent Process for Research (HRP-090)" Sections 5.5 and 5.6.

Response:

Prospective subjects will be allotted appropriate time to discuss amongst themselves and appropriate parent / guardians with or without the research examiner present, if needed. Prospective subjects will have permission to come back later to inform the research examiner of their decision if they need additional time to think and discuss outside of the clinic prior to committing. Prospective subjects can take as long as needed to make their decision and voice their concerns, there will be no time restriction or pressure from the research team.

28.4 Describe any process to ensure ongoing consent, defined as a subject's willingness to continue participation for the duration of the research study.

Response:

Subjects will be asked at every visit if they wish to continue in their current research study. The subject will have full autonomy to withdraw or continue. There will be appropriate documentation that will be signed by the subject to ensure consent was given.

- 28.5 Indicate whether you will be following "SOP: Informed Consent Process for Research (HRP-090)." Pay particular attention to Sections 5.4-5.9. If not, or if there are any exceptions or additional details to what is covered in the SOP, describe:

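### Section 22 bars all use of withdrawn participants' data, and says both that the data are destroyed and that they are kept; the exclusion can bias the primary comparison of treatment duration if withdrawal is related to duration

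*Protocol*

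**What the plan says.** Participants are randomised after consent and before bonding (section 12.1: "A randomization protocol will be followed in order to assign subjects to 1 of 2 study groups"). The primary outcome is the number of months from bonding to appliance removal at T1, once a Class I molar relationship is reached (sections 1.0 and 5.1). Section 19.1 compares the arms with an independent t-test or, if the data are not normal, a Wilcoxon rank-sum test.

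Section 22 then fixes what happens to the data of those who withdraw:

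- Section 22.2, for a patient who decides to withdraw: "any collected data of the subject will be destroyed and discarded accordingly".
- Section 22.3, for subjects who withdraw: "It will not be used in the research study however as the data will not be complete". The next sentence reads "It will be maintained for approximately 3 years".

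The withdrawal grounds in 22.1 include "Do not come regularly as needed for the study" and "Voluntarily want to leave the study or cease treatment". Section 28.4 adds: "Subjects will be asked at every visit if they wish to continue in their current research study". Section 13.2 says that the expected 5 +/- 1 months depends on compliance. It also says that the study ends before orthodontic treatment does, and section 12.4 takes treatment duration from the clinic's patient records.

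**The concern.** There are two problems.

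The first is a contradiction. Data cannot be both destroyed and kept for 3 years. If 22.2 is followed, no later analysis plan can recover what was lost.

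The second is an exclusion after randomisation, written as a rule and so not a detail left open for an SAP. Someone who leaves the research but stays in treatment at the clinic may later have the appliance removed at Class I correction. The primary outcome would then exist and the start date would be known, yet 22.3 discards both.

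What is at stake is the primary comparison. If slower patients are more likely to withdraw, and the extent or mechanism differs between arms, the arm that lost them looks faster than it is. If the mechanism is the same in both arms and the arms are equal, no false difference arises. A true difference can still shrink, because the slower arm loses more people.

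**Working it through.** **Inputs from the protocol.** 16 per arm, significance level 0.05, power 80%, standardised effect d = 1.02366 (section 19.2). A two-sided test is assumed from the no-difference hypothesis in 2.2. The protocol gives no withdrawal rate, no SD and no link between withdrawal and duration, so every loss scenario below is an assumption.

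**Step 1: the plan's own figure.** For a two-sample t-test with n per arm, the noncentrality is d × √(n/2) on 2n − 2 degrees of freedom. At n = 16 this is 1.02366 × √8 = 2.895 on 30 df, with critical value 2.042, and power is 0.800. The stated sample size is reproduced exactly and holds no reserve.

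**Step 2: loss unrelated to duration.** There is no bias. The same formula gives:

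| Per arm | 16 | 15 | 14 | 13 | 12 |
|---|---|---|---|---|---|
| Power | 80.0% | 77.2% | 74.1% | 70.7% | 66.9% |

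**Step 3: loss related to duration, one arm only.** Simulation with 16 v 16 normal durations and 40,000 replicates. The k participants in one arm with the highest withdrawal score are removed, where the score has correlation rho with duration, and a t-test is run on those left. Results are for k = 1 to 4. The power column assumes that the slower arm loses them and that the true difference is 1.02 SD.

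| rho | Spurious difference, equal arms | Type I error | Power |
|---|---|---|---|
| 0 | 0.00 SD | 5% | see step 2 for loss in both arms |
| 0.3 | 0.04–0.12 SD | 5–6% | 76–63% |
| 0.5 | 0.06–0.20 SD | 5.5–8% | 74–57% |
| 1 (exactly the slowest leave) | 0.12–0.40 SD | 7–21% | 71–42% |

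The last row is an upper limit.

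**Step 4: the same rule in both arms.** Assume monthly visits, a mean of 5 months in the faster arm, and 25% of those still uncorrected leaving at each visit from month 6. With equal arms the bias is 0.00. With a true difference of 1.02 SD:

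| Assumed SD (months) | Observed difference | Lost, faster / slower arm (of 16) | Power |
|---|---|---|---|
| 1 | 0.92 SD | 0.7 / 2.6 | 70% |
| 1.5 | 0.87 SD | 1.3 / 4.2 | 63% |
| 2 | 0.82 SD | 1.9 / 5.4 | 57% |

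Random loss of the same sizes would alone give about 75%, 71% and 67%. Roughly half of the fall in power is therefore smaller numbers, and the rest is selection.

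**Step 5: the per-visit question alone.** A slower patient is asked more often whether to continue. At an assumed 3% leaving per monthly visit, in one arm only, the shift is 0.03–0.06 SD and type I error stays at 5%. That is negligible.

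**The case against.** The strongest reply is that 22.3 is only part of the cause. A participant who leaves with no removal date has no value for a t-test or rank-sum test, whatever 22.3 says, and deleting the sentence would not bring that person back. This stands. The rule does its own damage where a true removal date exists and is thrown away; for the others, the endpoint definition and the choice of test do the excluding.

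The second reply is that the bias is conditional and thinly supported. This also stands. Sections 13.2 and 22.1 make a link plausible through compliance and attendance, but they do not size it, and the one mechanism that can be built from the stated procedures is negligible (step 5).

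A reader might infer that the trial's result will be biased, or biased towards a particular appliance. The documents do not support that: they give no withdrawal rate, no difference between arms and no direction. A reader might equally infer that equal numbers lost from each arm make the comparison safe. That does not follow, because it also needs the same selection mechanism and spread in both arms. It is also not stated whether 22.3 covers removal by the investigator under 22.1, although its reason, incomplete data, would fit both.

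The trial's pilot status does not remove the point, since 2.2 states a hypothesis to be tested and 19.2 powers it.

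**Conclusion.** The point holds in this form. The contradiction between 22.2 and 22.3, and the bar on use, are certain from the text. Bias in the primary comparison is possible and of unknown size. Unrelated loss costs power only: 80% falls to 74% at 14 per arm and 67% at 12. With 1 to 4 of 16 lost from one arm, a correlation of 0.5 gives a spurious 0.06–0.20 SD and 5.5–8% type I error; the upper limit is 0.12–0.40 SD and 7–21%. These figures rest on normal durations and assumed losses, none of which the protocol supplies. It should be fixed, because the change is cheap before data are collected and destruction cannot be undone afterwards.

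**What to change.** - **22.2 and 22.3:** reconcile destruction with retention. Delete the sentence barring use. Retain and use data collected up to withdrawal unless permission for that use is withdrawn, and make the consent text match. State whether the provision also covers removal under 22.1.
- **Removal dates:** where permission allows, take the date of removal at Class I correction from the clinic records for those who leave the research but continue treatment, and include them in the primary comparison as allocated.
- **19.1:** for bonded participants with no such date, add an analysis of all bonded participants as allocated, with time to correction censored at the last visit, for example Kaplan-Meier curves and a generalised Wilcoxon test. Show it beside the planned t-test or rank-sum test, labelled *participants with a removal date only*. The planned test stays, so the hypothesis about mean duration in 2.2 need not change.
- **Reporting:** give withdrawals by arm, timing and reason, including those lost between randomisation and bonding, who have no start date and so appear only there.

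The cost is wording, matching consent text and a little analysis work; no visits or patients are added. With no withdrawals the censored test has about 79% power against 80%. It is not immune: if exactly the slowest 1 to 4 leave one arm, its type I error is about 6–11% (assuming censoring at 20–90% of each person's own duration). That is why both results should be shown.

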23.0 Risks to Subjects*

23.1 List the reasonably foreseeable risks, discomforts, hazards, or inconveniences to the subjects related to their participation in the research. Consider physical, psychological, social, legal, and economic risks. Include a description of the probability, magnitude, duration, and reversibility of the risks.

NOTE: Breach of confidentiality is always a risk for identifiable subject data.

Response:

Since our subjects will be receiving orthodontic treatment by orthodontic residents under the supervision of faculty members who are adequately trained orthodontists, we will have inherent minimal risks which are routine in orthodontic treatment. These risks include:

- Tooth discomfort
- Tissue abrasion from the appliances
- White spot lesions on enamel structure of teeth (due to plaque build up and lack of hygiene)
- Root resorption
- Periodontal issues (gingivitis, inflammation, periodontitis, can develop due to plaque and lack of hygiene)
- Discomfort (due to tooth movement and biomechanical forces)
- Halitosis (due to plaque retention and lack of hygiene)
- Reduced esthetics (Orthodontic appliances are bonded to the labial tooth surfaces which can be un-esthetic to patients, development of spacing mesial to the appliances as distalization of the buccal segments occurs)

Page 36 of 49

- TMJ issues
- Broken appliances (bracket, wires, springs)
- Infection (lack of oral hygiene)
- Allergies to the materials used for treatment (Including common allergies to nickel and latex)
- 23.2 Describe procedures performed to lessen the probability or magnitude of risks, including procedures being performed to monitor subjects for safety.

Response:

- All biomechanical orthodontic forces will be standardized and delivered within standard of care parameters, keeping forces continuous but light to reduce any potential risk of pain, discomfort, and root resorption.
- Subjects will be given appropriate oral hygiene tools (floss threaders, proxy brushes, toothbrushes, plaque disclosing tablets) and instruction on how to maintain oral health prior to starting orthodontic treatment. This will ensure that each subject is aware of the hygiene required during treatment, which will reduce the risk of white spot lesions, periodontal issues, and halitosis. Reduced inflammation will also provide more comfort to the subject during treatment.
- To reduce risk of discomfort and abrasion, subjects will be given orthodontic wax to place on brackets or wires that give them any discomfort and will be instructed on how to use the wax. Wires and retainers will be trimmed accordingly, and the subject will be asked prior to leaving if there is anything bothering them to reduce discomfort.
- At each adjustment visit, subjects will be assessed clinically extra orally and intraorally to evaluate any changes and look for pathology, inflammation, abrasions, and any tooth damage (white spot lesions, fractures, caries). Tissues will be assessed for inflammation and erythema. Radiography will be taken to assess the root anatomy, alveolar bone level, TMJ anatomy and screen for any pathology)
- Subjects will be able to communicate with the research examiner if there are any issues between adjustment visits (discomfort, broken appliance, pain, difficulty chewing/eating, psychological issues). They will be either seen for an emergency visit to address the concern or guided via teledentistry communication to resolve the issue if possible.
- Subjects will have their medical and dental history updated at every visit (including their initial screening visit) to ensure that all appropriate changes in their health are on record. They will be asked about any concerns or issues they are having, which will be recorded and addressed accordingly.

Page 37 of 49

- Regarding subjects who have or develop an allergic reaction to nickel or latex, there will be appropriate changes made to their treatment to prevent the allergy.
- 23.3 If applicable, indicate **which procedures** may have risks to the subjects that are currently unforeseeable.

Response:

This current study is minimal risk. The general risks are a broken appliance and the minimal risk of additional radiation exposure.

23.4 If applicable, indicate which research procedures may have risks to an embryo or fetus should the subject be or become pregnant.

Response: If the patient becomes pregnant, their participation will be terminated due to the possible risk of radiographic exposure to the fetus.

23.5 If applicable, describe risks to others who are not subjects.

Response: N/A

24.0 Potential Benefits to Subjects*

24.1 Describe the potential benefits that individual subjects may experience by taking part in the research. Include the probability, magnitude, and duration of the potential benefits. Indicate if there is no direct benefit.

NOTE: Compensation cannot be stated as a benefit.

Response:

Patients presenting for orthodontic treatment seek to improve their dentition in both function and esthetics. By participating in this study, they will be achieving their goals through the treatment mechanics that will be utilized. Spaces will be closed, appropriate Angle's classification will be achieved, appropriate overjet and overbite will be achieved, all the while maintaining teeth in the healthy boundaries of the alveolar bone.

25.0 Compensation for Research-Related Injury

- N/A: The research procedures for this study do not present risk of research related injury (e.g. survey studies, records review studies). This section does not apply.
- 25.1 If the research procedures carry a risk of research related injury, describe the available compensation to subjects in the event that such injury should occur.

Response:

Research related injury will be compensated appropriately per University at School of Dental Medicine policies.

25.2 Provide a copy of contract language, if any, relevant to compensation for research related injury.

NOTE: If the contract is not yet approved at the time of this submission, submit the current version here. If the contract is later approved with different language regarding research related injury, you must modify your response here and submit an amendment to the IRB for review and approval.

Response: N/A

26.0 Economic Burden to Subjects

26.1 Describe any costs that subjects may be responsible for because of participation in the research.

NOTE: Some examples include transportation or parking.

Response:

Patients will be required to cover the following costs by participating:

- Fees associated with comprehensive orthodontic treatment
- No additional costs will be required in order to participate in the study

N/A: This study is not enrolling subjects, or is limited to records review procedures only. This section does not apply.

27.0 Compensation for Participation

27.1 Describe the amount and timing of any compensation to subjects, including monetary, course credit, or gift card compensation.

Response:

- N/A: This study is not enrolling subjects, or is limited to records review procedures only. This section does not apply.
- N/A: There is no compensation for participation. This section does not apply.

28.0 Consent Process

28.1 Indicate whether you will be obtaining consent.

NOTE: This does not refer to consent documentation, but rather whether you will be obtaining permission from subjects to participate in a research study. Consent documentation is addressed in Section 29.0.

\boxtimes	Yes	(If yes, Provide responses to each question in this Section)
	No	(If no, Skip to Section 29.0)

28.2 Describe where the consent process will take place. Include steps to maximize subjects' privacy.

Response:

Consent will take place at the University at Buffalo School of Dental Medicine in the Orthodontic Clinic, in the privacy of a closed-in room outside of the orthodontic clinic. Prospective subjects will be able to voice any questions or concerns with absolute privacy, prior to providing their consent to participate in the study.

28.3 Describe how you will ensure that subjects are provided with a sufficient period of time to consider taking part in the research study.

NOTE: It is always a requirement that a prospective subject is given sufficient time to have their questions answered and consider their participation. See "SOP: Informed Consent Process for Research (HRP-090)" Sections 5.5 and 5.6.

Response:

Prospective subjects will be allotted appropriate time to discuss amongst themselves and appropriate parent / guardians with or without the research examiner present, if needed. Prospective subjects will have permission to come back later to inform the research examiner of their decision if they need additional time to think and discuss outside of the clinic prior to committing. Prospective subjects can take as long as needed to make their decision and voice their concerns, there will be no time restriction or pressure from the research team.

28.4 Describe any process to ensure ongoing consent, defined as a subject's willingness to continue participation for the duration of the research study.

Response:

Subjects will be asked at every visit if they wish to continue in their current research study. The subject will have full autonomy to withdraw or continue. There will be appropriate documentation that will be signed by the subject to ensure consent was given.

- 28.5 Indicate whether you will be following "SOP: Informed Consent Process for Research (HRP-090)." Pay particular attention to Sections 5.4-5.9. If not, or if there are any exceptions or additional details to what is covered in the SOP, describe:
 - The role of the individuals listed in the application who are involved in the consent process
 - The time that will be devoted to the consent discussion
 - Steps that will be taken to minimize the possibility of coercion or undue influence

• Steps that will be taken to ensure the subjects' understanding

Resp	onse:
	We have reviewed and will be following "SOP: Informed Consent Process for Research (HRP-090)."
Non-	English Speaking Subjects
	N/A: This study will not enroll Non-English speaking subjects. (Skip to Section 28.8)
28.6	Indicate which language(s) other than English are likely to be spoken/understood by your prospective study population or their legally authorized representatives.
	NOTE: The response to this Section should correspond with your response to Section 8.4 of this protocol.
Resp	onse: Spanish, Arabic, French, Haitian

28.7 If subjects who do not speak English will be enrolled, describe the process to ensure that the oral and written information provided to those subjects will be in that language, how you will ensure that subjects are provided with a sufficient period of time to consider taking part in the research study, and any process to ensure ongoing consent. Indicate the language that will be

NOTE: Guidance is provided on "SOP: Informed Consent Process for Research (HRP-090)."

Response:

used by those obtaining consent.

During the orthodontic screening appointment, prospective subjects will be assessed on their proficiency in English. If they find difficulty understanding (reading, writing, and speaking) English, their preferred language of communication will be noted. Appropriate language translators will be made available to subjects that are not English speaking. All documentation will be translated accordingly so that the patient has full comprehension of the documents and consents they are to sign.

During the recruitment phase of the study, the language translator will be present during each of the discussions with the research subjects. Appropriate extra time will be allotted for translation communication between the research examiner and subjects, to ensure that the subjects have adequate time to understand the information. English langue will be used to obtain consent.

Page 41 of 49

Cognitively Impaired Adults

- N/A: This study will not enroll cognitively impaired adults. (Skip to Section 28.9)
- 28.8 Describe the process to determine whether an individual is capable of consent.

Response:

Adults Unable to Consent

N/A: This study will not enroll adults unable to consent. (*Skip to Section 28.13*)

When a person is not capable of consent due to cognitive impairment, a legally authorized representative should be used to provide consent (Sections 28.9 and 28.10) and, where possible, assent of the individual should also be solicited (Sections 28.11 and 28.12).

28.9 Describe how you will identify a Legally Authorized Representative (LAR). Indicate that you have reviewed the "SOP: Legally Authorized Representatives, Children, and Guardians (HRP-013)" for research in New York State.

NOTE: Examples of acceptable response includes: verifying the electronic medical record to determine if an LAR is recorded.

Response:

- We have reviewed and will be following "SOP: Legally Authorized Representatives, Children, and Guardians (HRP-013)."
- 28.10 For research conducted outside of New York State, provide information that describes which individuals are authorized under applicable law to consent on behalf of a prospective subject to their participation in the research. One method of obtaining this information is to have a legal counsel or authority review your protocol along with the definition of "legally authorized representative" in "SOP: Legally Authorized Representatives, Children, and Guardians (HRP-013)."

Response: N/A

28.11 Describe the process for assent of the adults:

• Indicate whether assent will be obtained from all, some, or none of the subjects. If some, indicate which adults will be required to assent and which will not.

Response: N/A

• If assent will not be obtained from some or all subjects, provide an explanation of why not.

Response: N/A

28.12 Describe whether **assent of the adult** subjects will be documented and the process to document assent.

NOTE: The IRB allows the person obtaining assent to document assent on the consent document using the "Template Consent Document (HRP-502)" Signature Block for Assent of Adults who are Legally Unable to Consent.

Response: N/A

Subjects who are not yet Adults (Infants, Children, and Teenagers)

- □ N/A: This study will not enroll subjects who are not yet adults. (Skip to Section 29.0)
- 28.13 Describe the criteria that will be used to determine whether a prospective subject has not attained the legal age for consent to treatments or procedures involved in the research under the applicable law of the jurisdiction in which the research will be conducted (e.g., individuals under the age of 18 years). For research conducted in NYS, review "SOP: Legally Authorized Representatives, Children, and Guardians (HRP-013)" to be aware of which individuals in the state meet the definition of "children."

NOTE: Examples of acceptable responses include: verification via electronic medical record, driver's license or state-issued ID, screening questionnaire.

Response:

Subject's medical record, screening forms and discussion with parent/guardian will be utilized to assess subject's legality to consent to treatment / procedures involved in research.

28.14 For research conducted outside of New York State, provide information that describes which persons have not attained the legal age for consent to treatments or procedures involved the research, under the applicable law of the jurisdiction in which research will be conducted. One method of obtaining this information is to have a legal counsel or authority review your protocol along the definition of "children" in "SOP: Legally Authorized Representatives, Children, and Guardians (HRP-013)."

28.15 Describe whether parental permission will be obtained from:		
Response:		
One parent even if the other parent is alive, known, competent, reasonably available, and shares legal responsibility for the care and custody of the child.		
Both parents unless one parent is deceased, unknown, incompetent, or not reasonably available, or when only one parent has legal responsibility for the care and custody of the child.		
☐ Parent permission will not be obtained. A waiver of parent permission is being requested.		
NOTE: The requirement for parent permission is a protocol-specific determination made by the IRB based on the risk level of the research. For guidance, review the "CHECKLIST: Children (HRP-416)."		
28.16 Describe whether permission will be obtained from individuals other than parents, and if so, who will be allowed to provide permission. Describe your procedure for determining an individual's authority to consent to the child's general medical care.		
Response:		
If there is no known living parent, then the next individual to give permission / consent for the subject to participate in research would have to be the legal guardian. To assess legitimacy of legal guardianship, appropriate documentation will need to be provided by said individual. Once documentation has been verified, authority to consent will be approved.		
28.17 Indicate whether assent will be obtained from all, some, or none of the children. If assent will be obtained from some children, indicate which children will be required to assent.		
Response:		
Assent will be obtained from all adolescent subjects in the research study.		
28.18 When assent of children is obtained, describe how it will be documented.		
Response:		
Assent will be document in the same manner as consent from the legal guardian / parent. Appropriate documentation will provide all information for the subject, al questions will be answered, and patient will have freedom to speak for themselves.		

keeping.

on their participation. Signature will be gathered from the child / adolescent, and paperwork will be scanned into the patient's electronic health record for safe

